#### 5.2.1.4 Time to Onset and Exposure Adjusted Incidence

For summary tables that summarize time-at-risk exposure adjusted incidence, the following definitions will be used.

###  Part A + B:

Part A + B Exposure-adjusted incidence (EAI) of an AE event is defined as the number of events divided by the total duration of exposure of the subjects at risk during the entire Part A + B treatment, which is computed as following:

Part A + B Exposure Adjusted incidence rate (e) =  $n*100/EY_{A+B}$ 

where:

- *n* is the number of subjects *with an event*
- *Exposure year* (*EY*A+B) = (sum of time to onset of the event)/365.25
- Time to onset of the event = date of onset of event date of the first APL-2 dose +1

For subjects without the event, time to onset is censored as follows: Time to onset of the event = last dose date + 56 days - first APL-2 dose date +1

For subjects who experienced the same event on multiple occasions:

*Time to onset of the event = date of onset at the first occasion – first APL-2 dose date +1* 

#### Part B:

Part B EAI will be determined for Part B TEAE (i.e. AE with a start date on or after the date of first 1080 mg APL-2 dose). It is defined as the number of events divided by the total duration of exposure of the subjects at risk during Part B treatment, which is computed as following:

Part B Exposure Adjusted incidence rate (e) =  $n*100/EY_B$ 

where:

- *n* is the number of subjects with an event
- *Exposure year* (*EYB*) = (sum of time to onset of the event)/365.25
- Time to onset of the event = date of onset of event date of the first 1080 APL-2 dose +1

For subjects without the event, time to onset is censored as follows: *Time to onset of the event = last dose date + 56 days – first 1080 mg APL-2 dose date +1* 

For subjects who experienced the same event on multiple occasions: Time to onset of the event = date of onset at the first occasion - first 1080 mg APL-2 dose date +1

### 5.2.1.5 Adverse Event Listings

An AE data listing of all AEs collected on study, including verbatim term, preferred term, treatment, severity, and relationship to treatment will be provided. Serious Adverse Events (SAEs), adverse events of special interest, and details of subjects withdrawing due to adverse events will also be listed. A Study Day in Part A + B relative to Part A Baseline, a

Study Day in Part B relative to Part B Baseline, and the duration of AEs will be included in listings.

#### 5.2.1.6 Adverse Event Summary Tables

Adverse Event tables will include summaries for TEAE in Part A + B and for TEAE in Part B.

#### **Overall Summary Table**

An overall AE summary will present the number of events and the frequency of subjects by cohort and by study part (Cohort 1 wAIHA Part A + B / Cohort 1 wAIHA Part B / Cohort 2 CAD Part A + B / Cohort 2 CAD Part B) with the following categories:

- any TEAE
- any TEAE considered as least possibly related to study drug (evaluated by the investigator as Possibly Related, Probably Related, Definitely Related, or Unknown)
- any serious TEAE
- Maximum severity TEAE of mild, moderate, severe, life threatening, and death, i.e. a subject with TEAEs at different intensities will be summarized at the most severe intensity
- any TEAE of special interest
- any TEAE leading to study drug discontinuation
- any TEAE leading to death

The total number of unique terms within subjects will also be presented in each of the categories above, counting each TEAE PT only once within each subject. Additionally, the total number of unique terms within cohorts will be presented in each of the categories above, counting each TEAE PT only once within each cohort.

#### Summary Tables by SOC and PT

The following tables will be presented with the number of events and the number/percent of subjects by cohort and by study part (Cohort 1 wAIHA Part B / Cohort 1 wAIHA Part A+ B / Cohort 2 CAD Part B / Cohort 2 CAD Part A + B).

- Non-ISR TEAEs by SOC and preferred term, including exposure-adjusted incidence
- TEAEs regarded as at least possibly related to study drug by SOC and preferred term, including exposure-adjusted incidence
- Injection Site Reaction TEAEs by SOC and preferred term, including exposure-adjusted incidence
- Serious AEs by SOC and preferred term, including exposureadjusted incidence

The summaries above will be ordered by alphabetical SOC and descending order of total event count of the term in Part A + B for the PT within each SOC.

### Summary Tables by SOC, PT, and Maximum Severity

The following will also be tabulated with the number/percent of subjects by cohort and study part (wAIHA Part B / wAIHA Part A + B / CAD Part B / CAD Part A + B):

- TEAEs by SOC, preferred term, and maximum severity
- Serious TEAE by SOC, preferred term, and maximum severity
- TE Protocol AESIs by SOC, preferred term, and maximum severity
- Related TE Protocol AESIs (regarded as at least possibly related to study drug) by SOC, preferred term, and maximum severity
- TEAE of Special Search Categories by SOC, preferred term, and maximum severity
- Related TEAE of Special Search Categories (regarded as at least possibly related to study drug) by SOC, preferred term, and maximum severity

The summaries above will be ordered alphabetical SOC and alphabetical PT within each SOC.

#### 5.2.2 Clinical Laboratory Tests

#### 5.2.2.1 Clinical Laboratory Normalization

Some laboratory parameters will be collected by central and local laboratories. In the cases where a visit's sample is collected on both central and local labs, the central lab result will be presented in the TLF. In the cases where only local labs are available, the local lab data will be normalized using the method developed by Stein (Stein, 1992, 2001).

The procedure for the normalization of local lab results will be followed for all local lab values with different normal ranges than the central lab:

- 1. Convert all parameters' units from different local lab units to SI units.
- 2. Impute the local normal ranges as shown below.
- Assume there is one central Lab (LabConnect) and all NRLO(CL) and NRHI(CL) are sourced from Appendix IV of LabConnect's Central Scope of Work 1.0 11 July 2017 and gender/age specific normal ranges are used when applicable.
  - i. If the NRLO is missing and NRHI is not missing, then do the following:

NRLO=NRHI \* NRLO(CL) / NRHI(CL)

ii. If the NRHI is missing and NRLO is not missing, then do the following:

NRHI=NRLO \* NRHI(CL) / NRLO(CL)

iii. If both NRLO and NRHI are missing prior to the imputations above, do the following:

*NRLO=min (all NRLO including CL)* 

and

NRHI=max (all NRHI including CL),

Apellis Pharmaceuticals, Inc.
Protocol: APL2-CP-AIHA-208
Part B Long Term Extension Statistical Analysis Plan

Version 1.0

using sex- or age-specific normal ranges when applicable

4. The following formula will be used to convert local lab value at observation level to central lab value:

$$Central \ value \ = NRLO(CL) + \frac{local \ value - NRLO}{NRHI - NRLO} \times (NRHI(CL) - NRLO(CL))$$

where:

- NRLO: Low normal range for local lab
- NRHI: High normal range for local lab
- NRLO(CL): Low normal range for central lab
- NRHI(CL): High normal range for central lab
- 5. Check for negative Lab values after the normalization. If so, do the following:
  - a. Set negative value to Zero, or
  - b. Use Upper Scale Formula: Central Value = Local value \* NRHI (CL)/NRHI, or
  - c. Use Lower Scale Formula: Central Value = Local value \* NRLO (CL)/NRLO

(Use a, or b or c as appropriate).

6. Perform the analyses (e.g., CFB) as usual.

#### 5.2.2.2 Potentially Clinically Significant

Clinical laboratory test values are potentially clinically significant (PCS) if they meet either the low or high PCS criteria listed in Table 3 below.

### 5.2.2.3 Clinical Laboratory Listings

Non-efficacy Chemistry, Non-efficacy Hematology, Coagulation, Urinalysis, non-PD Cytometry, and Miscellaneous (which includes the Anti-APL-2 AB

Assay) results will be listed for Safety Set. Additionally, separate PCS listings for subjects with at least one PCS result will be presented for each of the above laboratory categories.

Listings of all lab results with their corresponding changes from baseline (Change from Part A + B Baseline and Change from Part B Baseline for assessments after the first 1080 mg APL-2 dose) will be presented. Change from Part A + B Baseline will be considered as the pre-dose measure on Study Day 1, or the screening assessment if missing the Study Day 1 assessment. Part B Baseline will be considered as the last assessment before the first 1080mg APL-2 dose for each subject. Potentially Clinically Significant laboratory values will be identified in listings per Section 5.2.2.2, using high and low flags.

#### 5.2.2.4 Clinical Laboratory Summary Tables

Non-efficacy Chemistry, Non-efficacy Hematology, Coagulation, Urinalysis, non-PD Cytometry, and Miscellaneous results will be summarized separately.

#### **Descriptive Statistics:**

Descriptive statistics will be presented by cohort (Cohort 1 wAIHA / Cohort 2 CAD) on Safety Set as follows:

- Part A + B: Part A + B Baseline, all post-baseline scheduled visits through the end of study, and change from Part A + B Baseline.
- Part B: Part B Baseline, all scheduled visits in Part B (i.e. on and after the first 1080 mg APL-2 dose), and change from Part B Baseline.

### **PCS Frequencies:**

The frequency of PCS values at all scheduled visits on-study will be presented by cohort (Cohort 1 wAIHA / Cohort 2 CAD) on the safety set. At each visit, the number of subjects evaluable will be presented with the frequency and percent of subjects with low, normal, and high PCS results. The percentages will be calculated relative to the number of subjects with available baseline values and at least 1 post-baseline assessment. The numerator is the total number of subjects by-visit with at least 1 post-baseline PCS value and denominator is the number of subjects with evaluable assessment in the cohort at the respective visit.

Version 1.0

#### 5.2.3 Vital Signs

#### 5.2.3.1 Potentially Clinically Significant

Vital sign values are potentially clinically significant (PCS) if they meet either the low or high PCS criteria listed in Table 4 below.

Table 4: Criteria for Potentially Clinical	ly Significat	it Vital Signs
--	---------------	----------------

Value	Parameter	Low	High
Observed	Systolic Blood Pressure	≤ 80	≥165
	(mmHg)		
	Diastolic Blood Pressure	≤ 40	≥95
	(mmHg)		
	Pulse (bpm)	≤40	≥120
	Temperature (°C)		≥38

\*mmHg=millimeters of mercury, bpm=beats per minute, °C=degrees Celsius

#### 5.2.3.2 Vital Signs Listings

Listings of all vital sign results with their corresponding changes from baseline (Change from Part A + B Baseline and Change from Part B Baseline for assessments after the first 1080 mg APL-2 dose) will be presented. Change from Part A + B Baseline will be considered as the last pre-dose measure on Study Day 1, or the screening assessment if missing the Study Day 1 assessment. Part B Baseline will be considered as the last assessment before the first 1080mg APL-2 dose for each subject. Potentially Clinically Significant vital sign values will be identified in listings per Section 5.2.3.1 above, using high and low flags. 5.2.3.3 Vital Signs Summary Tables

#### **Descriptive Statistics:**

Descriptive statistics will be presented by cohort (Cohort 1 wAIHA / Cohort 2 CAD) on Safety Set as follows:

- Part A + B: Part A + B Baseline, all post-baseline scheduled visits through the end of study and change from Part A + B Baseline.
- Part B: Part B Baseline, all scheduled visits in Part B (i.e. on and after the first 1080 mg APL-2 dose), and change from Part B Baseline.

### **PCS Frequencies:**

The frequency of PCS values at all scheduled visits on-study will be presented by cohort (Cohort 1 wAIHA / Cohort 2 CAD) on the safety set. At each visit, the number of subjects evaluable will be presented with the frequency and percent of subjects with low, normal, and high PCS results. The percentages will be calculated relative to the number of subjects with available baseline values and at least 1 post-baseline assessment. The numerator is the total number of subjects by-visit with at least 1 post-baseline PCS value and denominator is the number of subjects with evaluable assessment in the cohort at the respective visit.

### 5.2.4 Electrocardiogram (ECG)

ECG data is not scheduled to be collected in Part B Long-term Extension Phase; therefore, ECG summarizes will not be summarized. ECG data that was collected after visit 15 of Part A will be presented in listings.

#### 5.2.5 Physical Examination

Physical examination data will be summarized in listing(s).

#### 5.3 Exploratory Efficacy and Pharmacodynamic Analyses

While the primary objective of this study is safety, exploratory efficacy and pharmacodynamic analyses will be presented. All efficacy listings will include all subjects in the Intent-to-Treat Set. All PD listings will include all subjects in the PD Set. All efficacy summaries will be evaluated on the Intent-to-Treat Set. All pharmacodynamic summaries will be evaluated on the PD Set.

#### 5.3.1 Packed Red Blood Cell (PRBC) Transfusions

## 5.3.1.1 Transfusions Per Month

PRBC Transfusions per month will be derived for Part A + B Baseline, Part A + B, Part B Baseline, and Part B as follows:

• Part A + B Baseline Transfusions Per Month =

# of transfusions in 365 days prior to first APL-2 dose\*28 365

• Part A + B Transfusions Per Month =

# of transfusions during Part A and Part B\*28 # of days during Part A and Part B

• Part B Baseline Transfusions Per Month =

# of transfusions in 365 days prior to first 1080 mg APL-2 dose\*28 365

• Part B Transfusions Per Month =  $\frac{\# of transfusions during Part B*28}{\# of days during Part B}$ 

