#### Part B: Long-Term Extension Phase:

Following Visit 15 (Week 48), subjects who elect to continue in the Part B Long-Term Extension Phase will return to the site at 12-week intervals indefinitely until the subject discontinues or the development program is terminated.

Specific procedures for each visit are listed in the Study Flow Chart for the Long-Term Extension Phase in Table 2 in Section 3.3.2.

At Visit 15 (Week 48), subjects electing to enter the Part B Long-Term Extension Phase will begin an APL-2 dose regimen of APL-2 1,080 mg twice weekly (with potential to escalate to APL-2 1,080 mg every 3 days). When switching from the Part A Core Study Phase formulation and dose of APL-2 (270 mg/d or 360 mg/d) to the formulation and dose intended for use in the Long-Term Extension Phase (APL-2 1,080 mg twice weekly), subjects should return to the site for APL-2 administration training and to conduct Dose Transition Visits 1, 2 and 4 weeks after the new dose is initiated and perform the procedures outlined in Appendix Section 8.1.

Subjects who plan on continuing in the Part B Long-Term Extension Phase should be instructed to skip their daily Part A Core Study Phase Dose the day prior to Visit 15 (i.e., the subject should not self-administer APL-2 on Day 335).

**Note:** The first dose of APL-2 1,080 mg should be administered at the Visit 15 (Day 336), with Dose Transition Visits at Week 49, Week 50, and Week 52. Some subjects may enter the Part B Long-Term Extension Phase prior to the availability of the sorbitol formulation. These subjects should continue on their Part A Core Study Phase dose into the Part B Long-Term Extension Phase. These subjects will transition to the Long-Term Extension Phase dose at the next scheduled visit at which the sorbitol formulation and dose is available, and should schedule Visits T1, T2, and T3 1, 2 and 4 weeks following the visit at which the sorbitol dose is initiated. These subjects should be instructed to skip their Part A dose the day before the visit at which the APL-2 1,080 mg twice weekly dose regimen is scheduled to be initiated.

Subjects who discontinue treatment early should complete one Early Termination Follow-up Visit (ETFU) 6 weeks after discontinuation of treatment, and one Early Termination (ET) Exit Visit 6 weeks after the ETFU as outlined in Appendix 8.1.

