#### 4.2 Definitions

#### 4.2.1 Study Day

#### Part A + B:

Study Day 1 for Part A + B will be the day a subject takes the first dose of APL-2, which will be calculated as:

For events that occurred on the day of or after administration of the first APL-2 dose:

Part A + B Study Day = visit date – date of first APL-2 dose + 1

For events that occurred on days before administration of the first APL-2 dose:

Part A + B Study Day = visit date – date of first APL-2 dose

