## Part B:

Part B is considered all visits and assessments from the date of first 1080 mg APL-2 dose through the date of last APL-2 dose.

For events that occurred on the day of or after administration of the first 1080 mg APL-2 dose in Part B Long Term Extension Phase:

Part B Study Day = visit date - date of first 1080 mg APL-2 dose + 1

For events that occurred on days before administration of the first 1080 mg APL-2 dose:

Part B Study Day = visit date – date of first 1080 mg APL-2 dose

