#### 4.2.2 Baseline and Change from Baseline

Summary tables will present: 1) change from Part A baseline summaries assessments during Part A + B and 2) change from Part B baseline

Apellis Pharmaceuticals, Inc. Protocol: APL2-CP-AIHA-208 Part B Long Term Extension Statistical Analysis Plan

Version 1.0

summaries assessments during Part B. This section outlines the definitions for baseline and change from baseline for all safety and efficacy assessments collected during study visits, except for transfusions (see Section 5.3.1).

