#### Part B

Part B baseline for this study will be derived as the last measure prior to the first 1080 mg APL-2 dose.

Unless indicated otherwise Part B change from baseline (Part B CFB) will be calculated as follows for after Part B Study Day 1:

Part B CFB = Visit Result – Part B Baseline Result

Percent change from baseline (Part B PCFB) will be calculated as follows:

Part B PCFB (%) = 100\*(Visit Result – Part B Baseline Result)/ (Part B Baseline Result) Where Part B Baseline is the last assessment prior to the first 1080 mg APL-2 dose on Part B Study Day 1.

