## 5.3.1.3 Transfusions Listings

The following listings will be prepared:

- Transfusion History, for all transfusions recorded in the 365 days prior to enrollment
- On-Study Transfusions, for all transfusions recorded on-study, where study part will be specified
- PRBC Transfusions and Units Per Month which will include:
  - *Part A + B PRBC*:
    - Number of Days during Part A + B Baseline Period
      (365 days) and Number of Days during Part A and B
    - Part A + B Baseline Transfusions Per Month and Part A
      + B Transfusions Per Month
    - Part A + B Baseline Units Per Month and Part A + B Units Per Month
  - **Part B PRBC**:
    - Number of Days during Part B Baseline Period (365 days) and Number of Days during Part B
    - Part B Baseline Transfusions Per Month and Part B Transfusions Per Month
    - Part B Baseline Units Per Month and Part B Units Per Month

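### The Part B transfusion baseline uses a fixed 365-day look-back, so for a switch to 1080 mg at Day 336 it takes in 30 days before any APL-2, and part of the fall at the start of APL-2 can be credited to the switch

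*SAP*

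**What the plan says.** All references are to the Part B SAP (08 Nov 2022) unless stated.

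- **Transfusion baseline.** Section 5.3.1.1 takes the number "of transfusions in 365 days prior to first 1080 mg APL-2 dose", times 28/365. Section 5.3.1.2 does the same for units. The listing in 5.3.1.3 gives the period as a constant: "Number of Days during Part B Baseline Period (365 days) and Number of Days during Part B".
- **Timing of the switch.** Section 4.2.1 states "Study Day 1 for Part A + B will be the day a subject takes the first dose of APL-2". Section 3.3 puts the planned switch at Visit 15: "The first dose of APL-2 1,080 mg should be administered at the Visit 15 (Day 336"). For subjects who reach Part B before the sorbitol formulation is available, 3.3 says "These subjects should continue on their Part A Core Study Phase dose into the Part B Long-Term Extension Phase"; they switch at a later visit.
- **Part B period.** Section 4.2.1: "Part B is considered all visits and assessments from the date of first 1080 mg APL-2 dose through the date of last APL-2 dose".
- **Other Part B baselines.** Section 4.2.2: "Part B baseline for this study will be derived as the last measure prior to the first 1080 mg APL-2 dose". That section covers assessments "collected during study visits, except for transfusions (see Section 5.3.1"), so transfusions have their own rule.
- **Output.** Section 5.3.1.4 tabulates Part B baseline and Part B rates together, by cohort, for transfusions and units. It plans no change from Part B baseline and no rate for Part A alone.

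**The concern.** For laboratory values, FACIT, LASA and PD, the Part B baseline is the last value before the first 1080 mg dose. Part B then shows what happens after the move from daily dosing to 1080 mg. A transfusion rate needs a period rather than a single value, so a separate rule is reasonable. But nothing in 5.3.1 keeps that period within time on APL-2, and for an on-schedule switch 365 days is longer than the time on APL-2.

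The number of RBC transfusions is a listed efficacy endpoint. Protocol 7.3 expects APL-2, if efficacious, to reduce transfusion dependency, which would make the rate before APL-2 higher than the rate in Part A. Pre-APL-2 days would then raise the Part B baseline. An unchanged need for transfusion after the switch would look like a further gain, and a loss of effect would be understated by the same amount. Early and late switchers would also sit in one column under different definitions.

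**Working it through.** The documents give no transfusion rates and no figure to reproduce. The day count below follows from the SAP; the rates are assumptions.

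**Step 1: pre-APL-2 days in the window.** Day 1 is the first APL-2 dose, so a switch on Day s follows s - 1 days of APL-2.

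Pre-APL-2 days = max(0, 365 - (s - 1))

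The planned day is 336. The Part A flow chart in the protocol allows 7 days either side of Visit 15.

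| Switch day | Days on APL-2 in window | Pre-APL-2 days | Share of 365 |
|---|---|---|---|
| 329 | 328 | 37 | 10.1% |
| 336 | 335 | 30 | 8.2% |
| 343 | 342 | 23 | 6.3% |
| 365 | 364 | 1 | 0.3% |
| 366 or later | 365 | 0 | 0% |

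**Step 2: effect on the baseline.** Let r0 be the rate before APL-2 and r1 the rate on APL-2, both per 28 days and constant, with r1 the same in Parts A and B. For a Day 336 switch:

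Part B baseline = (30 x r0 + 335 x r1)/365

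Excess over r1 = (30/365) x (r0 - r1) = 0.082 x (r0 - r1)

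| r0 | r1 | SAP baseline | Part B rate | Excess |
|---|---|---|---|---|
| 1 | 0 | 30/365 = 0.082 | 0 | 0.082 |
| 1 | 0.1 | 63.5/365 = 0.174 | 0.10 | 0.074 |
| 2 | 1 | 395/365 = 1.082 | 1.00 | 0.082 |
| 4 | 1 | 455/365 = 1.247 | 1.00 | 0.247 |
| 1 | 1 | 365/365 = 1.000 | 1.00 | 0 |

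As a share of the SAP baseline, the apparent fall is 0.082/1.082 = 7.6% for r0 = 2, r1 = 1 and 0.247/1.247 = 19.8% for r0 = 4, r1 = 1. For one subject, a single transfusion in those 30 days and none afterwards gives 28/365 = 0.077 per month at baseline against 0 in Part B. If r0 is below r1, the sign reverses.

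**Step 3: baseline limited to days on APL-2.** For a Day 336 switch the rate becomes (count on Days 1 to 335) x 28/335. Under the same assumptions this equals r1, and the apparent change is 0 in every row.

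**The case against.** The case for leaving the rule alone has several parts.

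- **No change score is planned.** Section 5.3.1.4 shows two rates side by side, so any fall is one the reader infers. This stands, although setting a baseline beside a post-baseline rate invites that comparison.
- **The effect is small and conditional.** It is 0.082 x (r0 - r1), from assumed rates. This stands. A reader might infer from the r1 = 0 case that Part B would generally show a false fall of 100%. That percentage comes only from a zero on-treatment rate; with r1 = 1 and r0 = 2 the figure is 7.6%.
- **The number affected is unknown.** Subjects may stay on the Part A dose past Day 336. The visit windows in 4.2.3 target Part A Visits 16 and 17 at Days 420 and 504, against 378 and 420 in the Part A SAP (4.1.2). That suggests, without proving it, that some subjects were expected to switch well after Day 336.
- **Other outputs help.** Transfusion history and on-study transfusions are listed (5.3.1.3), and the Part A SAP (5.3.1) gives a Part A rate, though not limited to subjects who rolled over. A careful reader could detect the problem.
- **A uniform 365 days matches the Part A + B baseline.** True, but that window lies wholly before APL-2. For a Day 336 switch the Part B window does not lie wholly on one side of the first APL-2 dose, and the same 30 days enter both baselines.

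Two stronger readings are not supported. One is that the table would show a fall that never happened. When r0 exceeds r1 the fall is real, but it occurred at the start of APL-2 and is placed at the switch. The other is that the 30 days are a full, untreated screening period with active hemolysis throughout. Screening is only required to take place within 30 days of dosing, the eligibility criteria do not bar steroids, and Hb below 11 g/dL is a screening criterion rather than a value known for each day. These are pre-APL-2 days and no more can be said.

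**Conclusion.** The point holds as a misattribution. For a switch at Day 336, 30 of the 365 baseline days (8.2%; 37 to 23 days across the visit window) predate APL-2, and nothing in 5.3.1 removes them. The day count depends only on the SAP's definitions. The direction depends on r0 exceeding r1, and the size, 0.082 x (r0 - r1) per 28 days, assumes constant rates that the documents do not give. For subjects switching on Day 366 or later there is no effect.

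The absolute effect is modest. It can still matter where on-treatment rates are near zero, because each cohort has a target of 12 subjects and only those who receive 1080 mg enter the Part B analysis sets. The analysis is exploratory and descriptive: no test, error rate or decision rule is affected, and the Part A + B comparison is untouched. What is at stake is how a listed efficacy endpoint is read across the switch. The derivation should be corrected, but the point does not undermine the study.

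**What to change.** In 5.3.1.1 and 5.3.1.2, define the Part B baseline as the number of transfusions (units) in the last D days before the first 1080 mg dose, times 28/D, where

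D = min(365, date of first 1080 mg dose - date of first APL-2 dose).

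In 5.3.1.3, list D for each subject in place of the constant 365 for Part B. Dividing by actual days follows the Part A SAP (5.3.1), which uses the number of days in the study part.

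The cost is a line of SAP wording in each section and one derivation change. No new data are needed, because the revised baseline uses only on-study transfusions. Baseline length will vary slightly between subjects (335 days for a Day 336 switch, 365 from Day 366), and the Part B comparison may look slightly less favourable. The baseline will still average up to a year on APL-2, including the first weeks of treatment, so it remains a period average and not a value taken just before the switch. The table footnote should say so.
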